5.2 STUDY ENDPOINTS

Primary endpoints:

1. Primary Efficacy Endpoint Freedom from AT/AF clinical recurrence on follow-up visits AND less than 30 seconds of AT/AF on a 1 month continuous electrocardiographic monitor at 6 and 12 months.
2. Primary Safety Endpoint - Acute procedural complications and total mortality.

Secondary Endpoints

1. Freedom from AF/AT after >1 procedure.
2. Freedom from AF/AT on antiarrhythmic drugs.
3. AF burden (% time) on continuous monitoring at 6 and 12 months.
4. Procedural parameters: total procedure, fluoroscopy, total RF ablation time (first procedure), and total extent of ablated LA tissue.
5. Clinical/partial success: less than 25% AF burden on a continuous event monitor at 6 and 12 months from ablation procedure.
6. Sub-acute procedural complications (within 30 days).
7. Recurrence as persistent or paroxysmal AF, or flutter after 1 or 2 procedures.

8. LA function on Doppler echocardiography (LA strain^{114ab}) at 12 months.
9. Incidence and mechanisms of atrial flutters.
10. Cardiovascular hospitalizations and
11. QOL as determined by AFEQT questionnaire.

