5.5 STUDY PROCEDURES

SCREENING/BASELINE

1. Initial assessment.

After signing informed consent, the following data will be collected; a significant medical history and recent targeted physical exam, electrocardiogram (EKG), echocardiogram within one year prior to the procedure for evaluation of cardiac structure, and function, and laboratory tests. In addition, a review of medications that patient is taking (limited to AAD and anticoagulants), and a quality of life (QOL) questionnaire especially developed for AF (AFEQT)¹¹³ will be filled out by patients.

Screening assessments performed pre-consent signature that are completed under standard of care can be included as viable source documents for patient study inclusion/exclusion and may be collected to screen potential study patients.

2. Pre-procedural imaging.

Imaging prior to enrollment is required to rule out structural heart disease and, as needed, to rule out the presence of LA appendage thrombus. *Ruling out LAA thrombus can be performed by the following: TEE, CT or MRI within 48 hours of the*

procedure; at least one month of oral anticoagulation prior to the procedure; or documented prior procedures of LAA occlusion or ligation. For ruling out structural heart disease, either a cardiac MRI, CT or transthoracic echocardiogram within 1 year prior to participation in the study is sufficient. Documentation by exception (ie. no LAA thrombus documented on imaging report) is permitted for determination of eligibility. Left atrial diameter and estimated left atrial volume will be obtained from any of these diagnostic modalities. There is no specific requirement for a pre-ablation CT or MR, since anatomical details of the LA can be obtained intra-procedurally with current mapping systems.

3 Randomization.

Randomization should take place after confirmation that all inclusion/exclusion criteria are met and measurements of LA volume are obtained. Patients will be randomized in a 1.15:1 fashion (to account for an 85% technical feasibility of the VOM procedure) to receive either VOM-PV or the conventional PVAI. Patients will be blinded to the randomization outcome.

PROCEDURE/DAY 0:

1 PVAI procedure

As part of a conventional catheter ablation of AF the following will be performed, all considered standard of care:

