Subjects who have a miniaturized, implantable rhythm recording device (such as Medtronic LinQ and others) or an implantable pacemaker/defibrillator may have the continuous rhythm data obtained from that device, and may forego the portable recorder.

Patients will fill out the AFEQT¹¹³ QOL questionnaire. Additionally, echocardiographic assessment of LA function (LA ejection fraction, strain^{114ab}) will be performed by a central reader at Houston Methodist Hospital.

—

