- Enrollment as AF or AT –for MARS-AF trial only.
- Pre-existing low voltage scar and extent of low-voltage scar after ablation procedure (divided in tertiles).

Primary Outcome. Hypothesis tests for the equality of two proportions (unpooled standard errors) will be employed for determining whether or not the VOM success rate is significantly greater than the success rate for PVAI. The test statistic is a z-score which is standard normal distributed and the relevant lookup critical values (percentage points) are listed in the interim analysis section for group sequential designs. From a post-hoc perspective, we may use the stratified Mantel-Haenszel odds ratio test of proportions if we learn that success rates track with a particular covariate, such as LA volume or AF duration, and the strata weights are not highly imbalanced.

Secondary Outcomes. The secondary outcomes are listed below along with their corresponding storage location (various tables or Excel .csv files on output after report generation). Model building strategies (MBS) will be employed using univariate and multivariable regression models for post-hoc analyses of secondary outcomes. During MBS, univariate predictors whose $p < 0.25$ will be selected as multiple variable model candidates. MBS regression methods may include linear, logistic, Poisson, and Cox proportional hazards (PH) along with regression diagnostics using the relevant goodness-of-fit criteria, residuals, variance inflation factors (VIF), ROC-AUC, and assumption-checking techniques (e.g. normally-distributed standardized residuals for linear regression). Regression diagnostics for linear regression will include estimation and filtering of overly influential records based on residuals, standardized residuals, deletion residuals, Cook's distance, leverage, DFFITS, DFBETAS, and VIFs. Regression diagnostics for logistic and Poisson regression will include filtering on Pearson, deviance, and leverage residuals and the Hosmer-Lemeshow test for logistic regression GOF. Cox PH regression diagnostics will include Schoenfeld and Nelson-Aelen residuals, and possible employment of stratified models when the PH assumption fails.

The table below lists the primary outcomes which are to be analyzed during each interim analysis, as well as the secondary outcomes which will be analyzed and reported prior to all DSMB review meetings.

Primary Endpoints	EDC Pages	Data Fields

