8. Incidence and mechanisms of atrial flutters.	
 12 lead ECG page AE page Evaluation for repeat procedure page 	
 Date of occurrence Type of flutter (typical vs atypical)
9. Cardiovascular hospitalizations and QOL.	
 Hospitalizations SAEs QOL 	
 Total # of CV related hospitalizations QOL score

Use of propensity scores in multivariate models. An ideal goal for observational etiological

studies is to allocate randomly subjects into different treatment groups in order to guarantee on average that there are no systematic differences in covariates between groups.¹²⁰ After randomization, there is nevertheless a possibility for observing large differences in confounders which may lead to bias in results. The propensity score provides a scalar summary of covariate information and is defined as the propensity (probability) that a subject's covariate profile represents subjects truly assigned to a given treatment group. Propensity scores based on significantly different confounder variables can be used to create a quasi-randomized experiment with adjustment to the treatment effect. We will assess the role of propensity scores in prediction models in order to reduce the effects of baseline factors that may be significantly different among subjects in different treatment groups. Firstly, we will identify baseline covariates which are significantly different across treatment groups (using t-tests with skew-zero transformed covariates or Mann-Whitney tests). Significant covariates will be incorporated into a logistic regression model ($y=0$ PVAI, 1-VOM-PV) to generate subject-specific logits, which are normally-distributed.^{121, 122} Treatment-subject-specific logits will then be used for matching subjects across the treatment groups in order to construct a sample of subjects with balanced covariates. We suspect that propensity matching will not be required to tackle the problem of extreme confounder differences, but will nevertheless evaluate the effect of propensity matching prior to logistic regression to determine treatment effect possibly adjusted for age.

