7.0 STUDY ORGANIZATION

7.1 SCHEDULE OF EVENTS

Visit ID	1	2	3	4	5	6	7	8	9
Procedure	screen/ baseline	procedure day 0	prior to discharge	7 days (± 3)	30 day FU (±10) 1mo	90 day FU (±30d) 3mo	180 day FU (±60d) 6mo	9 mo FU (±30d)	360 day FU (±60d) 12 mos.
Informed Consent (prior to study specific procedures)	X								
Eligibility Checklist (PMH, medications, verification of Inclusion and exclusion criteria)	X								
General Medical History & Cardiovascular History with CHADS2-VASC Score)	X								
LAA thrombus exclusion Transesophageal Echocardiogram (within 48 hours) or anticoagulation/LAA exclusion)	X ⁽ⁱ⁾								
Cardiac MRI or CT or Echocardiogram (showing structure & function within 1 year)	X ^(m)								
Randomization	X								
Targeted Physical Exam	X				X	X	X	X	X
12 lead EKG	X	X pre- procedure	X		X	X	X	X	X
Laboratory: CBC, Serum creatinine, and INR – (INR only if patient is taking warfarin ^(g))	X								
AF Quality of Life Questionnaire (AFEQT)	X						X	X	X
Pre-procedure 3D Mapping^(b,j)		X							
VOM Procedure w/ ETOH Injection and Post ethanol map		X ⁽ⁱ⁾							
PVAI Procedure		X							
Post Procedure 3 D Mapping		X ^(c,j)							
Follow-Up Phone Call⁽ⁱ⁾				X					
3-4 Week EKG (Event Monitor)^(d,n)							X		X
Echocardiogram , Central Reader ([name])									X ^(k)
Repeat Procedure allowed^(e)						X	X	X	
AAD Therapy	If appl.	If appl.	If appl.	If appl.	If appl.	Stop AAD ^(a)			
Anticoagulation	X	X	X	X	X	X	X	X	X
Adverse Events	X	X	X	X	X	X	X	X	X

Footnote Key

- (a) Must be in sinus rhythm prior to stopping AAD, may stop if clinically indicated
- (b) Required for both VENUS-AF and MARS-AF groups. For subjects in VENUS-AF, there should be little to no scarring for first procedure. For subjects in MARS-AF group and study patients requiring repeat procedures, maps will assess pre-existing extent of previous ablation lesions and presence or absence of PV reconnection.
- (c) To delineate extent of scar in both PVAI alone and PVAI/VOM groups.
- (d) Continuous 4 week EKG monitoring, will take place at month 6, and 12
- (e) Repeat procedures will be allowed if certain criteria met
- (f) Seven day follow-up phone call to assess post procedure symptoms.
- (g) Baseline INR must be within 24 hours prior to procedure for patients taking warfarin;
- (h) Not applicable.
- (i) For patients randomized to receive VOM ethanol infusion, and who have a vein of Marshall that can be cannulated.

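### AFEQT is collected at baseline, but no baseline-adjusted treatment comparison is prespecified, so whether the baseline score enters the model is left to post-hoc selection

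*Combined protocol and SAP*

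**What the plan says.** Section 5.2 lists "QOL as determined by AFEQT questionnaire" as the eleventh secondary endpoint. Section 5.5 collects it at screening, naming "a quality of life (QOL) questionnaire especially developed for AF (AFEQT". Section 5.6 repeats it at 6 and at 12 months ("Patients will fill out the AFEQT¹¹³ QOL questionnaire").

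Section 6.0 covers the analysis:

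- The endpoint table has a row "9. Cardiovascular hospitalizations and QOL". The data field for quality of life is a QOL score, with no visit, no definition of change and no baseline term.
- The text on secondary outcomes states: "Model building strategies (MBS) will be employed using univariate and multivariable regression models for post-hoc analyses of secondary outcomes". Predictors with univariate p < 0.25 "will be selected as multiple variable model candidates". Linear regression is among the permitted methods. The pool of predictors is not listed, and no rule says which candidates stay in the final model.
- The propensity-score text adds a second data-driven route: "Firstly, we will identify baseline covariates which are significantly different across treatment groups". Those covariates then feed a propensity model.

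Two other places bear on the point. The cross-over items of sections 5.7 and 5.8 say that secondary endpoints are computed by the arm first assigned. Section 5.1 says that randomisation (in MARS) is stratified by recurrence as flutter or as AF.

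**The concern.** When a score is measured before randomisation and again at follow-up, the usual treatment comparison adjusts the follow-up score for the baseline score. The plan collects what this needs but does not commit to it. An analyst could report raw follow-up scores, change scores or an adjusted model, and could choose after seeing the data.

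Two things are at stake. The first is precision: a comparison without the baseline score has a larger variance whenever the two scores are correlated. A chance baseline imbalance of d SD would also shift an unadjusted difference by about r × d SD. The second is that the reported estimate is not fixed in advance, so a reader cannot tell whether the model was chosen before or after the result was known.

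**Working it through.** **Inputs.** VENUS has 180 + 156 = 336 patients and MARS 37 + 32 = 69 (synopsis; the MARS power statement in section 6.0 uses 33 + 33). The documents give no AFEQT SD, effect size or correlation. Assumptions: r from 0.2 to 0.6; equal SD at baseline and follow-up; both scores available for every patient; an effect of 0.3 SD, for illustration only.

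**The plan's own figure.** The plan states no power for AFEQT. Its VENUS sample size serves the primary endpoint. Simulating the three looks with the stated boundaries gives power 0.910 against the stated 0.909. The sample size is therefore sound as an input, but that figure says nothing about AFEQT.

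**Step 1: variance.** Take the variance of the difference in raw follow-up scores as 1. ANCOVA then has 1 − r². The equivalent unadjusted sample size is 336/(1 − r²). The difference detectable with 80% power, unadjusted, is (1.960 + 0.842) × √(1/180 + 1/156) = 2.802 × 0.1094 = 0.306 SD; ANCOVA multiplies this by √(1 − r²). Power at 0.3 SD is Φ(0.3/(0.1094 × √(1 − r²)) − 1.960).

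| VENUS | Variance | Cut | 1/(1 − r²) | Equivalent N | Detectable (SD) | Power at 0.3 SD |
|---|---|---|---|---|---|---|
| Unadjusted | 1.00 | – | – | 336 | 0.306 | 78% |
| ANCOVA, r = 0.2 | 0.96 | 4% | 1.04 | 350 | 0.300 | 80% |
| ANCOVA, r = 0.3 | 0.91 | 9% | 1.10 | 369 | 0.292 | 82% |
| ANCOVA, r = 0.4 | 0.84 | 16% | 1.19 | 400 | 0.281 | 85% |
| ANCOVA, r = 0.5 | 0.75 | 25% | 1.33 | 448 | 0.265 | 89% |
| ANCOVA, r = 0.6 | 0.64 | 36% | 1.56 | 525 | 0.245 | 93% |

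A change score has variance 2(1 − r), so ANCOVA relative to it is (1 − r²)/(2(1 − r)) = (1 + r)/2. That is 0.65 at r = 0.3 and 0.80 at r = 0.6, a cut of 35% and 20%.

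**Step 2: would the screen keep baseline AFEQT?** Suppose it is in the pool. By Fisher's z, with δ = atanh(r) × √(n − 3), the chance of p < 0.25 is Φ(δ − 1.150) + Φ(−δ − 1.150).

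- VENUS, r = 0.2: δ = 0.2027 × √333 = 3.70, chance 0.995. From r = 0.3 upward it is about 1.000.
- MARS, r = 0.2: δ = 0.2027 × √66 = 1.65, chance 0.69, so it fails 31% of the time.
- MARS, r = 0.3: δ = 0.3095 × √66 = 2.51, chance 0.91, so it fails 9% of the time.
- MARS, r = 0.5: chance above 0.99.

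Passing makes a predictor a candidate only. A further selection step, which the plan does not describe, could still drop it.

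**Step 3: what does the screen cost?** A simulation (4,000 runs per setting, 0.3 SD effect) kept the arm in the model and used baseline AFEQT as the only candidate, entered when it passed. Variances of the treatment estimate:

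| | Unadjusted | Screened | Always adjusted |
|---|---|---|---|
| VENUS, r = 0.5 | 0.01176 | 0.00865 | 0.00865 |
| MARS, r = 0.3 | 0.05643 | 0.05243 | 0.05254 |

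The loss comes from leaving baseline out. Screening it adds almost nothing to the variance.

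**The case against.** The strongest reply is that nothing in the plan rules out baseline adjustment. Linear multivariable regression is allowed, and the screen would nearly always pass baseline AFEQT in VENUS. The propensity text also attends to baseline imbalance. This stands in part. It shows that a good analysis is possible, not that one is promised. The propensity text is no substitute: it takes only covariates that differ significantly between arms, and its last step is a logistic regression, which does not fit a score.

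A reader might infer four stronger things that the documents do not support.

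- *That the analysis will not adjust for baseline.* The predictor pool is not listed, so baseline AFEQT is neither named nor excluded.
- *That the p < 0.25 screen is what loses precision.* Step 3 shows otherwise.
- *That screening makes the treatment comparison's error bars unreliable.* With no treatment effect, the arm kept in the model, 6 or 12 assumed candidates screened at p < 0.25 and r of 0.3 or 0.5, simulated type I error lay between 4.6% and 5.5% in VENUS and MARS, against a nominal 5%.
- *That the randomised arm might itself be screened out.* The model-building text does not exempt it, but sections 5.7 and 5.8 tie the secondary endpoints to the arm first assigned.

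The schedule of events also appears to show a 9-month AFEQT that the visit text in section 5.6 does not mention. This rests on column positions in an extracted table and is not counted here.

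**Conclusion.** The point holds as a gap in prespecification. The plan collects baseline AFEQT, names no AFEQT model and no main visit, and leaves the baseline term to a post-hoc procedure.

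The size is conditional. If baseline is left out, the comparison forgoes a variance reduction of 9% to 36% at an assumed correlation of 0.3 to 0.6, and only 4% at 0.2. In VENUS 9% to 36% is like having 336 patients instead of an effective 369 to 525. If baseline is a candidate and enters when it passes the screen, almost nothing is lost in VENUS. In MARS it could be missed in about 9% of trials at r = 0.3 and 31% at r = 0.2. What then remains is that the estimate is not fixed in advance.

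These figures rest on a correlation that the documents do not give, equal SDs and complete scores. Only a secondary endpoint is affected. The primary result, sample size and stopping boundaries do not change.

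**What to change.** Add to the secondary-outcomes text of section 6.0 that 12-month AFEQT is compared between arms, separately in VENUS and MARS, by ANCOVA with randomised arm and baseline AFEQT as fixed terms. In MARS, add the AF/flutter randomisation stratum. Use the same model at 6 months, with 12 months named as the main visit. Keep the p < 0.25 screen for exploratory prediction models, and say that it does not decide the terms of the treatment comparison.

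The cost is a sentence or two in the plan. The baseline scores and the stratum are already planned, so no patients, visits or data are added.

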- e. Documentation of RF time, time to perimitral block (if not already achieved), fluoroscopy time, LA instrumentation time, and procedure time.
- f. Baseline and Final LA voltage map (using any commercially available electroanatomical mapping systems). Measurement of baseline and Final LA scar surface area.

4. Effectiveness (Treatment) Failures

Effectiveness failures towards the primary endpoint will include the following (see Figure 8):

- a. Clinical recurrence of AF or AT after 3-months.
- b. Documented AF or AT of 30 seconds or more on EKG monitor at obtained at 6 and 12 months.
- c. Requirement of a repeat ablation procedure for recurrent AT-AF.
- d. Death.

VENUS and MARS patients who have a recurrence after 3 months post randomization will have a repeat procedure (PVAI). Patients will be deemed to be effectiveness failure for the primary efficacy endpoint of the trial after repeat procedures. Still, subjects will:

- a. Remain in the study for the purpose of all secondary endpoints: these include quality of life, AF burden on event monitoring, success after multiple procedures.
- b. Undergo all clinically necessary procedures and treatments, including prescription of antiarrhythmic therapy and additional procedures needed to control atrial fibrillation or flutter. A crossover VOM procedure will be offered to those randomized to PVAI after 2 in-study procedures.
- c. Data on such additional procedures or treatment will be collected in the Electronic Data Capture system (EDC).
- d. An additional secondary endpoint will be created: total number of procedures performed and requirement of antiarrhythmic drugs.

5. VENUS: Cross-over of patients initially randomized to PVAI only.

If a VENUS patient is originally randomized to conventional PVAI and experiences a treatment failure after a repeat procedure he or she may undergo an additional conventional PVAI ablation procedure during the study. Crossover to VOM ethanol will only be allowed after 2 procedures are performed in the setting of study participation. This is allowed because certain recurrent flutters are particularly suited to respond to VOM ethanol. The primary and secondary endpoints will be computed following their original randomization group.

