Results. A group sequential trial with sample sizes of N1=180 and N2=156 at the final look achieves 91% power to detect a difference of 0.18 between a treatment group success proportion of 0.56 and a control group success proportion of 0.38 at the 0.05 significance level (alpha) using a two-sided Z-Test (Unpooled). The table below lists the sample sizes required for 91% power.

Table 5. Sample size requirements for a group sequential trial based on 100,000 iterations.

Value	95% LCL	95% UCL	Target	Actual	95% LCL	95% UCL	Beta		
0.909	0.908	0.911	0.050	0.049	0.048	0.051	0.091		
----- Average Sample Size -----									
-- Given H0 -- -- Given H1 --									
N1	N2	Grp1	Grp2	Grp1	Grp2	Diff0	Diff1	P1 H1	P2
180	156	179	155	144	125	0.00	0.18	0.56	0.38

Efficacy Monitoring. We propose to monitor efficacy at two interim time points and one final time period (i.e., three “looks”) when primary outcome data (12 month follow-up) are available for 1/3, 2/3 and 3/3 of the total sample size of VENUS subjects. For the VENUS trial, these values are provide in the following table in terms of *information time*:

Table 6. Efficacy monitoring schedule for VENUS with cumulative sample size, significance boundaries and 95%CIs, and alpha- and beta-spending.

Accumulated primary outcomes for VENUS						
Look	Accumulated Sample Size -----					
	Percent	VOM	PVAI	Total		
1	33.33	60	52	112		
2	66.67	120	104	224		
3	100.00	180	156	336		

Significance Boundaries with 95% Simulation Confidence Intervals						
Look	----- Z-Value Boundary -----			----- P-Value Boundary -----		
	Value	95% LCL	95% UCL	Value	95% LCL	95% UCL
1	+/- 3.953	3.809	4.289	0.000	0.000	0.000
2	+/- 2.543	2.516	2.578	0.011	0.010	0.012
3	+/- 2.011	1.994	2.036	0.044	0.042	0.046

Alpha-Spending						
Look	----- Target -----			----- Actual -----		
	--- Signif. Boundary---	Spending	Spending	Proportion	Cum.	
Z-Value	P-Value	Function	Function		H1 Sims	H1 Sims
Look	Scale	Scale	Alpha	Alpha	Cum. Alpha	Outside Signif. Boundary
1	+/- 3.953	0.000	0.000	0.000	0.000	0.033
2	+/- 2.543	0.011	0.012	0.011	0.012	0.547
3	+/- 2.011	0.044	0.038	0.038	0.049	0.329
						0.909
		Spent	Spent	Boundary		Cum. Boundary

The hypothesis test applied at the k th look is a two-tailed test of equality of two independent proportions, functionally composed as

$$Z_k = \frac{\hat{p}_{1k} - \hat{p}_{2k}}{\sqrt{\frac{\hat{p}_{1k}(1-\hat{p}_{1k})}{n_{1k}} + \frac{\hat{p}_{2k}(1-\hat{p}_{2k})}{n_{2k}}}}$$

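### Secondary-outcome regressions are to filter out influential records with no cut-off and no unfiltered fit: common cut-offs raise type I error from 5% to about 10%, and estimates can be biased either way

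*Combined protocol and SAP*

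**What the plan says.** The Secondary Outcomes paragraph of Section 6.0 (Statistical Analyses) describes "univariate and multivariable regression models for post-hoc analyses of secondary outcomes". It names linear, logistic, Poisson and Cox models as possible methods.

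- **Linear:** diagnostics "will include estimation and filtering of overly influential records based on residuals", followed by standardized and deletion residuals, Cook's distance, leverage, DFFITS, DFBETAS and VIFs.
- **Logistic and Poisson:** diagnostics "will include filtering on Pearson, deviance, and leverage residuals".
- **Cox:** residual checks and "possible employment of stratified models when the PH assumption fails". No filtering is stated.

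The paragraph sets no cut-off for any measure, no limit on how many records may go, and no accompanying fit on all records. It describes no other inferential method for secondary outcomes. It has those outcomes analysed ahead of every DSMB review. Section 5.7 states, and Section 5.8 repeats: "The primary and secondary endpoints will be computed following their original randomization group".

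**The concern.** Filtering of records is most naturally read as taking them out of the model. The residual-based measures depend on the outcome, so randomised patients would leave the analysis partly because of how they responded.

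Two things follow. The refitted model sees an artificially small residual variance, so its p-values and intervals are too optimistic. And if flagged records are unevenly spread over the arms, the estimated effect moves. For AF burden, the patients most likely to be flagged are those with the most AF, who are the patients the outcome is meant to count. Outcome-dependent removal also sits badly with the commitment to analyse secondary endpoints by randomised group.

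At stake are the reported p-values, intervals and estimates for secondary outcomes such as AF burden, procedure times, LA strain and quality of life.

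**Working it through.** **Inputs from the documents.** VENUS has 180 VOM-PV and 156 PVAI patients, with success 0.56 vs 0.38 and three looks (Section 6.0, Tables 5 and 6). MARS has 37 and 32 (Synopsis). No significance level is given for secondary regressions, so 0.05 two-sided is assumed. Cut-offs, covariate effects and outcome distributions are also assumptions, because the plan gives none.

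**The plan's own figure.** No error rate is stated for the filtered regressions. The nearest design figure is this: "A group sequential trial with sample sizes of N1=180 and N2=156 at the final look achieves 91% power". The unpooled standard error is √(0.56×0.44/180 + 0.38×0.62/156) = √(0.001369 + 0.001510) = 0.0537, and 0.18/0.0537 = 3.355. At the final boundary, power is about Φ(3.355 − 2.011) = Φ(1.344) = 0.910. Simulating all three looks also gives 0.910, against 0.909 in Table 5. The figure reproduces. It concerns the primary test only.

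**Why deletion inflates error.** Take a normal outcome, scaled to unit variance, with residuals beyond ±c dropped and the model refitted. Let d = 2cφ(c) and E = [2Φ(c) − 1] − d. In large samples the ratio of the reported standard error to the true one is √(E/V), where V = E(1 + 2d) + d².

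- c = 2: d = 0.2160, E = 0.9545 − 0.2160 = 0.7385, V = 0.7385×1.4319 + 0.0466 = 1.1042. The ratio is √(0.7385/1.1042) = 0.818. The effective critical value is 1.96×0.818 = 1.603, so type I error is 10.9%.
- c = 2.5: ratio 0.919, type I error 7.2%.
- c = 3: ratio 0.974, type I error 5.6%.

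**Simulation, linear model.** Treatment plus two covariates, 180/156, normal outcome, no true effect, 6,000 trials per setting:

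| Rule | Type I error |
|---|---|
| All records kept | 5.1% |
| Cook's distance > 1 | 5.1% |
| Leverage > 2p/n | 5.2% |
| Deletion residual > 3 | 5.8% |
| Deletion residual > 2.5 | 7.3% |
| Deletion residual > 2 | 10.8% |
| Cook's distance > 4/n | 9.8% |
| DFFITS > 2√(p/n) | 9.8% |
| DFBETAS for treatment > 2/√n | 11.0% |
| All common cut-offs together | 16.4% (19% of records dropped) |

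The formula and the simulation agree at c = 2, 2.5 and 3. At the MARS size, the single rules on residuals > 2, Cook's distance > 4/n, DFFITS and DFBETAS give 10.7–11.2%. For skewed or zero-heavy outcomes at 180/156 these rules give 6.5–12.7%.

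**Simulation, logistic model** (3,000 trials per setting). Dropping standardized Pearson residuals > 2 gives type I error of 10.9% at a 38% event rate, 29.8% at 20% and 12.5% at 10%. The reason is arithmetic. Ignoring the small leverage adjustment, an event with fitted probability p has Pearson residual √((1 − p)/p), which exceeds 2 exactly when p < 0.20. Near a 20% rate, small differences in fitted probability decide whether an event is kept.

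**Effect on the estimate when there is a real effect.**

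- *Symmetric linear outcome:* 0.302 with all records and 0.301–0.302 after filtering. No bias.
- *Mostly-zero AF burden, AF in 15% vs 25%:* with all records the difference is −3.8 points (3.8/0.10 implies a mean burden of about 38% in those with AF). It becomes −1.9 with residual > 3, −1.5 with > 2.5, and −1.2 with > 2 or Cook's distance > 4/n. Another assumed burden distribution gives about −1.5 to −1.6 at the common cut-offs.
- *Second burden-like outcome, AF less rare:* −4.5 becomes −3.6 (residual > 2), −3.4 (Cook's distance > 4/n) and −1.7 with all rules, where power falls from 43% to 27%.
- *Logistic, Pearson > 2:* log odds ratio 0.74 becomes 0.82 (38% vs 56%), and 0.64 becomes 1.48 (15% vs 25%). In the latter case √(0.85/0.15) = 2.38 but √(0.75/0.25) = 1.73, so events tend to be removed from the lower-rate arm only.

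**After the fix.** With all records kept, type I error is 4.8–5.3% in the linear settings and 4.0–5.8% in the logistic ones. No Poisson model was simulated.

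**The case against.** The best defence has four parts.

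1. **Scope.** The plan calls these regressions post-hoc and says only that the methods may include the listed models. The primary analysis is an unpooled two-proportion Z-test that this step does not touch. This stands and limits the consequence. It does not remove it, because no other method for secondary outcomes is described.
2. **Unknown cut-off.** The wording may intend a strict threshold. Cook's distance above 1 does no harm, and a residual cut-off of 3 does little. This stands. A reader might infer that the plan doubles the false-positive rate. The documents do not support that as a property of the plan. Doubling describes one common choice with a near-normal outcome.
3. **A loose list.** VIFs appear among the grounds for filtering records, yet a VIF belongs to a predictor. That suggests a list of diagnostics rather than a deletion algorithm. It is a fair reading, but the text uses filtering for linear, logistic and Poisson models and only checks and stratification for Cox, so it does appear to distinguish the two.
4. **Safeguards.** Section 7.6 blinds analysis staff, and the plan asks for checks of normality and fit, which a linear model of zero-heavy burden should fail. Blinding does not help, because the inflation comes from a mechanical rule. The plan assigns no model to AF burden and does not say what follows a failed linear check.

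A reader might also infer that filtering always shrinks effects. That was seen only for burden-like outcomes, and logistic effects grew.

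**Conclusion.** The concern holds in a conditional form. The plan commits to filtering records in its linear, logistic and Poisson secondary-outcome models, without a cut-off or an unfiltered fit. Read as removal, and with common cut-offs, type I error for a near-normal linear outcome rises from 5% to about 10–11%. Across the settings tried it ranges from no inflation (Cook's distance > 1, leverage only) to about 30% (logistic, Pearson > 2, 20% rate). The upper figure is the largest seen and not a bound. Bias is absent for symmetric linear outcomes, toward zero for AF-burden-like outcomes, and away from zero in logistic models.

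These sizes rest on assumed cut-offs, covariate effects and outcome distributions. For hospitalisation counts the point is by analogy only. It would be wrong to infer that the primary efficacy result or efficacy stopping is at risk, since both rest on the two-proportion test. The weakness is that an unstated choice decides whether the secondary p-values are valid.

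**What to change.** Replace the filtering sentences for linear, logistic and Poisson models with text to this effect:

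- All randomised patients with data stay in every secondary-outcome model.
- Influence diagnostics are reported and used for data checks only.
- If model assumptions fail, use robust standard errors, a transformation, or a rank-based or two-part model.
- Any fit without flagged records is a labelled sensitivity analysis, with its cut-offs fixed in advance.

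Remove VIFs from the grounds for filtering records and keep them as a check on predictors.

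The cost is a change of SAP wording, with no effect on sample size, data collection or the primary analysis. Some intervals become wider.
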